## 12 LIST OF TABLES, FIGURES AND LISTINGS FOR THE IDMC, PRIMARY ANALYSIS AND FINAL ANALYSIS

The following table includes details of the tables, figures and listings to be included within each section of the eCTD. The eCTD section is shown in bold. The following validation methods may be used:

- Independent programming of numbers and manual review of format (IP)
- Independent programming by statistician of numbers and manual review of format (Stat IP)
- Manual review (MR)
- Code review (CR)

Note: Strikethrough tables are ones that were originally planned for primary and final analysis but will be excluded from the abbreviated CSR because of the termination of the study.

Table Number	Table Title	Included in IDMC meetings	Validation Method	Shell Number (if repeat)
Items in bold are not table titles but references to the section headings within eCTD.				
14.1	Demographic Data			
14.1.1.1	Subject Enrollment – Screened Set	1-4	IP	
14.1.1.2	Screen Failures – Screened Set	1-4	IP	
14.1.1.3	Inclusion/Exclusion Criteria – Screened Set	1-4	IP	
14.1.1.4	Analysis Sets – Pre-Screened Set	1-4	IP	
14.1.1.5	Cumulative proportion of information – Safety Analysis Set	1-4	IP	
14.1.1.6	Subject Disposition – Safety Analysis Set	1-4	IP	
14.1.1.7	Subject Disposition by Country – Safety Analysis Set	1-4	IP	14.1.1.6
<del>14.1.1.8</del>	<del>Visits/Assessments Affected by COVID-19 – Safety Analysis Set</del>		<del>IP</del>	
14.1.2.1	Demographics – Safety Analysis Set	1-4	IP	
14.1.3.1	Medical History Related to Centronuclear Myopathy (CNM) – Safety Analysis Set	1-4	IP	
14.1.3.2	Medical History Unrelated to Centronuclear Myopathy (CNM) – Safety Analysis Set	1-4	IP	14.1.3.1
14.1.4.1	Prior Medications – Safety Analysis Set	1-4	IP	
14.1.4.2	Concomitant Medications – Safety Analysis Set	1-4	IP	14.1.4.1
14.1.5.1	Treatment Exposure – Safety Analysis Set	1-4	IP	
14.1.5.2	Treatment Compliance – Safety Analysis Set	1-4	IP	
14.2	Pharmacodynamics and Exploratory Efficacy			

Table Number	Table Title	Included in IDMC meetings	Validation Method	Shell Number (if repeat)
14.2.1.1	PROMIS Questionnaire, Descriptive Statistics – Pharmacokinetic Set		IP	
14.2.2.1	CGI I Questionnaire, Frequency Table – Pharmacokinetic Set		IP	
14.2.2.2	CGI I Questionnaire, Responders – Pharmacokinetic Set		IP	14.2.2.1
14.2.3.1	PGI-C Questionnaire, Frequency Table – Pharmacokinetic Set		IP	14.2.2.1
14.2.3.2	PGI-C Questionnaire, Responders – Pharmacokinetic Set		IP	14.2.2.1
14.2.4.1	GAS Questionnaire, Frequency Table – Pharmacokinetic Set		IP	14.2.2.1
14.2.4.1	GAS Questionnaire, Responders – Pharmacokinetic Set		IP	14.2.2.1
14.2.5.1	Respiratory Function Tests, Descriptive Statistics – Pharmacokinetic Set	4	IP	14.2.1.1
14.2.5.2	Respiratory Function Tests, Shift Table – Pharmacokinetic Set	4	IP	
14.2.5.3	Explorative Bayesian Analysis for Respiratory Function Tests – Pharmacokinetic Set		Stat IP	
14.2.6.1	MyoGrip, Descriptive Statistics – Pharmacokinetic Set	4	IP	14.2.1.1
14.2.6.2	Explorative Bayesian Analysis for MyoGrip – Pharmacokinetic Set		Stat IP	14.2.5.3
14.2.7.1	MFM32, Descriptive Statistics – Pharmacokinetic Set	4	IP	14.2.1.1
14.2.7.2	Explorative Bayesian Analysis for MFM32 – Pharmacokinetic Set		Stat IP	14.2.5.3
14.2.8.1	Dysphagia Questionnaire, Descriptive Statistics – Pharmacokinetic Set	4	IP	14.2.1.1
14.2.9.1	Muscle Biopsy, Descriptive Statistics – Pharmacokinetic Set	4	IP	14.2.1.1
14.3	Safety Data			
14.3.1	Displays of Adverse Events			
14.3.1.1.1	Overall Summary of Adverse Events – Safety Analysis Set	1-4	IP	
14.3.1.2.1	Pre-Therapy AEs by System Organ Class and Preferred Term – Safety Analysis Set	1-4	IP	
14.3.1.2.2	TEAEs by System Organ Class and Preferred Term – Safety Analysis Set	1-4	IP	14.3.1.2.1
14.3.1.2.3	Treatment Related TEAEs by System Organ Class and Preferred Term – Safety Analysis Set	1-4	IP	14.3.1.2.1
14.3.1.2.4	Serious TEAEs by System Organ Class and Preferred Term – Safety Analysis Set	1-4	IP	14.3.1.2.1
14.3.1.2.5	TEAEs Leading to Treatment Withdrawal by System Organ Class and Preferred Term – Safety Analysis Set	1-4	IP	14.3.1.2.1
14.3.1.2.6	All AEs of Special Interest by System Organ Class and Preferred Term – Safety Analysis Set	1-4	IP	14.3.1.2.1

Table Number	Table Title	Included in IDMC meetings	Validation Method	Shell Number (if repeat)
14.3.1.3.1	TEAEs by System Organ Class, Preferred Term and Maximum Severity – Safety Analysis Set	1-4	IP	
14.3.1.3.2	Treatment Related TEAEs System Organ Class, Preferred Term and Maximum Severity – Safety Analysis Set	1-4	IP	14.3.1.3.1
14.3.1.4.1	TEAEs by System Organ Class, Preferred Term and Strongest Study Drug Relationship – Safety Analysis Set	1-4	IP	
14.3.2	Listings of Deaths, Other Serious and Significant Adverse Events			
14.3.2.1	Listing of Deaths – Safety Analysis Set	1-4	IP	
14.3.2.2	Listing of Serious TEAEs – Safety Analysis Set	1-4	IP	14.3.2.1
14.3.3	Narratives of Deaths, Other Serious and Certain Other Significant Adverse Events			
	Not Applicable			
14.3.4	Abnormal Laboratory Values			
14.3.4.1.1	Listing of Abnormal Laboratory Values	1-4	IP	
14.3.5	Laboratory Data			
14.3.5.1.1	Hematology Data, Descriptive Statistics – Safety Analysis Set	1-4	IP	14.2.1.1
14.3.5.1.2	Hematology Data, Shift Table – Safety Analysis Set	1-4	IP	14.2.5.2
14.3.5.2.1	Serum Chemistry Data, Descriptive Statistics – Safety Analysis Set	1-4	IP	14.2.1.1
14.3.5.2.2	Serum Chemistry Data, Shift Table – Safety Analysis Set	1-4	IP	14.2.5.2
14.3.5.3.1	Urinalysis Data, Frequency Table – Safety Analysis Set	1-4	IP	
14.3.5.4.1	Coagulation Data, Descriptive Statistics – Safety Analysis Set	1-4	IP	14.2.1.1
14.3.5.4.2	Coagulation Data, Shift Table – Safety Analysis Set	1-4	IP	14.2.5.2
14.3.5.5.1	Complement Data, Descriptive Statistics – Safety Analysis Set	1-4	IP	14.2.1.1
14.3.5.5.2	Complement Data, Shift Table – Safety Analysis Set	1-4	IP	14.2.5.2
14.3.6	Vital Signs			
14.3.6.1	Vital Signs, Descriptive Statistics – Safety Analysis Set	1-4	IP	14.2.1.1
14.3.7	ECG			
14.3.7.1	ECG Data, Descriptive Statistics – Safety Analysis Set	1-4	IP	14.2.1.1
14.3.7.2	ECG Data, Shift Table – Safety Analysis Set	1-4	IP	14.2.5.2
14.3.8	Physical Examination			
	Not Applicable			
14.4	Pharmacokinetics			
14.4.1.1	Pharmacokinetic Concentrations – Pharmacokinetic Set	1-4	IP	
14.4.2.1	Pharmacokinetic Parameters – Pharmacokinetic Set	4	IP	14.4.1.1
14.4.2.2	<del>Analysis of Dose Proportionality – Pharmacokinetic Set</del>		Stat IP	
14.4.2.3	<del>Analysis of Terminal Disposition Phase Rate Constant <math>\lambda_z</math> – Pharmacokinetic Set</del>		Stat IP	

Table Number	Table Title	Included in IDMC meetings	Validation Method	Shell Number (if repeat)
14.4.3.1	Anti-Drug Antibodies, Descriptive Statistics— Pharmacokinetic Set		IP	14.2.1.1 and/or 14.2.2.1
14.4.4.1	Metabolic Profiling (Blood), Descriptive Statistics— Pharmacokinetic Set		IP	14.2.1.1
14.4.4.2	Metabolic Profiling (Urine), Descriptive Statistics— Pharmacokinetic Set		IP	14.2.1.1

Figure Number	Figure Title	Included in IDMC meetings	Validation Method	Shell Number (if repeat)
14.2.1.1	PGI-C Questionnaire, Mean Profiles – Pharmacokinetic Set		IP	
14.2.1.2	PGI-C Questionnaire, Individual Profiles – Pharmacokinetic Set		IP	
14.2.2.1	Respiratory Function Tests, Mean Profiles – Pharmacokinetic Set		IP	14.2.1.1
14.2.2.2	Respiratory Function Tests, Individual Profiles – Pharmacokinetic Set		IP	14.2.1.2
14.2.3.1	MFM32, Mean Profiles – Pharmacokinetic Set		IP	14.2.1.1
14.2.3.2	MFM32, Individual Profiles – Pharmacokinetic Set		IP	14.2.1.2
14.3.5.1.1	Hematology, Mean Profiles – Safety Analysis Set	1-4	IP	14.2.1.1
14.3.5.1.2	Hematology, Individual Profiles – Safety Analysis Set	1-4	IP	14.2.1.2
14.3.5.2.1	Serum Chemistry, Mean Profiles – Safety Analysis Set	1-4	IP	14.2.1.1
14.3.5.2.2	Serum Chemistry, Individual Profiles – Safety Analysis Set	1-4	IP	14.2.1.2
14.3.5.4.1	Coagulation Data, Mean Profiles – Safety Analysis Set	1-4	IP	14.2.1.1
14.3.5.4.2	Coagulation Data, Individual Profiles – Safety Analysis Set	1-4	IP	14.2.1.2
14.3.5.5.1	Complement Data, Mean Profiles – Safety Analysis Set	1-4	IP	14.2.1.1
14.3.5.5.2	Complement Data, Individual Profiles – Safety Analysis Set	1-4	IP	14.2.1.2
14.3.6.1.1	Vital Signs, Mean Profiles – Safety Analysis Set	1-4	IP	14.2.1.1
14.3.6.1.2	Vital Signs, Individual Profiles – Safety Analysis Set	1-4	IP	14.2.1.2
14.3.7.1.1	ECG, Mean Profiles – Safety Analysis Set	1-4	IP	14.2.1.1
14.3.7.1.2	ECG, Individual Profiles – Safety Analysis Set	1-4	IP	14.2.1.2
14.4.1.1	Pharmacokinetic Concentrations, Mean Profiles on Linear and Semi-Logarithmic Scales – Pharmacokinetic Set	1-4	IP	
14.4.1.2	Pharmacokinetic Concentrations, Individual Profiles on Linear and Semi-Logarithmic Scales – Pharmacokinetic Set	1-4	IP	

Listing Number	Listing Title	Included in IDMC meetings	Validation Method	Shell Number (if repeat)
16.2	Subject Data Listings			
16.2.1	Discontinued Subjects			
16.2.1.1	Screen Failures – Screened Set	1-4	IP	
16.2.1.2	Inclusion/Exclusion Criteria – Screened Set	1-4	IP	
16.2.1.3	Study Completion – Safety Analysis Set	1-4	IP	
<del>16.2.1.4</del>	<del>COVID-19 Summary – Screened Set</del>		<del>IP</del>	
<del>16.2.1.5</del>	<del>COVID-19 Visit Log – Screened Set</del>		<del>IP</del>	
16.2.2	Protocol Deviations			
16.2.2.1	Protocol Deviations – Screened Set		IP	
16.2.3	Subjects Excluded From The Efficacy Analyses			
16.2.3.1	Analysis Sets – Pre-Screened Set	1-4	IP	
16.2.4	Demographic Data			
16.2.4.1	Informed Consent – Safety Analysis Set		IP	
16.2.4.2	Demographics – Safety Analysis Set	1-4	IP	
16.2.4.3	Medical History Related to CNM – Safety Analysis Set	1-4	IP	
16.2.4.4	Medical History Unrelated to CNM – Safety Analysis Set	1-4	IP	
16.2.4.5	Prior and Concomitant Medications – Safety Analysis Set	1-4	IP	
16.2.4.6	Prior and Concomitant Non-Drug Therapies and Procedures – Safety Analysis Set		IP	
16.2.5	Compliance and/or Drug Concentration Data			
16.2.5.1	Exposure and Compliance – Safety Analysis Set	1-4	IP	
16.2.5.2	Infusion Interruption / Infusion Rate Change – Safety Analysis Set	1-4	IP	
16.2.5.3	Pharmacokinetic Concentrations – Safety Analysis Set	1-4	IP	
16.2.5.4	Pharmacokinetic Parameters – Safety Analysis Set	4	IP	
16.2.6	Individual Efficacy Response Data			
<del>16.2.6.1</del>	<del>PROMIS – Pharmacokinetic Set</del>		<del>IP</del>	
<del>16.2.6.2</del>	<del>CGI I Questionnaire – Pharmacokinetic Set</del>		<del>IP</del>	
16.2.6.3	PGI-C Questionnaire – Pharmacokinetic Set		IP	
<del>16.2.6.4</del>	<del>GAS Questionnaire – Pharmacokinetic Set</del>		<del>IP</del>	
16.2.6.5	Respiratory Function Tests – Pharmacokinetic Set	4	IP	
<del>16.2.6.6</del>	<del>MyoGrip – Pharmacokinetic Set</del>	4	<del>IP</del>	
16.2.6.7	MFM32 – Pharmacokinetic Set	4	IP	
<del>16.2.6.8</del>	<del>Dysphagia Questionnaire – Pharmacokinetic Set</del>	4	<del>IP</del>	
<del>16.2.6.9</del>	<del>Muscle Biopsy – Pharmacokinetic Set</del>	4	<del>IP</del>	
16.2.7	Adverse Event Listings			
16.2.7.1	Adverse Events – Safety Analysis Set	1-4	IP	
16.2.8	Individual Laboratory Measurements and Other Safety			
16.2.8.1	Hematology – Safety Analysis Set	1-4	IP	
16.2.8.2	Serum Chemistry – Safety Analysis Set	1-4	IP	
16.2.8.3	Urinalysis – Safety Analysis Set	1-4	IP	

Listing Number	Listing Title	Included in IDMC meetings	Validation Method	Shell Number (if repeat)
16.2.8.4	Coagulation Data – Safety Analysis Set	1-4	IP	
16.2.8.5	Complement Data – Safety Analysis Set	1-4	IP	
16.2.8.6	Vital Signs – Safety Analysis Set	1-4	IP	
<del>16.2.8.7</del>	<del>Pregnancy Test – Safety Analysis Set</del>		<del>IP</del>	
16.2.8.8	ECG – Safety Analysis Set	1-4	IP	
16.2.8.9	Physical Examination – Safety Analysis Set	1-4	IP	
16.2.8.10	Neurological Examination – Safety Analysis Set	1-4	IP	
<del>16.2.8.11</del>	<del>Anti Drug Antibodies – Safety Analysis Set</del>		<del>IP</del>	
<del>16.2.8.12</del>	<del>Metabolic Profiling (Blood) – Safety Analysis Set</del>		<del>IP</del>	
<del>16.2.8.13</del>	<del>Metabolic Profiling (Urine) – Safety Analysis Set</del>		<del>IP</del>	
16.2.8.14	Liver ultrasound Including Hepatic Elastography – Safety Analysis Set		IP	
16.2.9	Abnormal Safety Results			
16.2.9.1	Abnormal Laboratory, ECG and Vital Sign Results – Safety Analysis Set	2-4	IP	

## 13 APPENDIX

### 13.1 PROMIS Scoring Tables

#### 13.1.1 ABILITY TO PARTICIPATE IN SOCIAL ROLES AND ACTIVITIES

Ability to Participate Social Roles and Activities 4a Adult version	
Raw Score	Scale Score
4	27.5
5	31.8
6	34.0
7	35.7
8	37.3
9	38.8
10	40.5
11	42.3
12	44.2
13	46.2
14	48.1
15	50.0
16	51.9
17	53.7
18	55.8
19	58.3
20	64.2

Ability to Participate Social Roles and Activities 8a Adult version	
Raw Score	Scale Score
8	25.9
9	29.7
10	31.3
11	32.6
12	33.6
13	34.5
14	35.3
15	36.2
16	36.9
17	37.7
18	38.5
19	39.3
20	40.2
21	41.1
22	42.0

Ability to Participate Social Roles and Activities 8a Adult version	
Raw Score	Scale Score
23	43.0
24	44.0
25	45.0
26	46.0
27	47.0
28	48.0
29	48.9
30	49.9
31	50.8
32	51.7
33	52.7
34	53.6
35	54.6
36	55.7
37	56.8
38	58.2
39	60.2
40	65.4

### 13.1.2 ANXIETY

Anxiety 8a Adult v1.0	
Raw Score	Scale Score
8	37.1
9	43.2
10	45.9
11	47.8
12	49.4
13	50.8
14	52.1
15	53.2
16	54.3
17	55.4
18	56.4
19	57.4
20	58.4
21	59.4
22	60.4
23	61.4
24	62.5
25	63.5
26	64.5
27	65.6
28	66.6
29	67.7
30	68.7
31	69.8
32	70.8
33	71.9
34	73.0
35	74.1
36	75.4
37	76.7
38	78.2
39	80.0
40	83.1

### 13.1.3 DEPRESSION

Depression 8a Adult v1.0	
Raw Score	Scale Score
8	38.2
9	44.7
10	47.5
11	49.4
12	50.9
13	52.1
14	53.2
15	54.1
16	55.1
17	55.9
18	56.8
19	57.7
20	58.5
21	59.4
22	60.3
23	61.2
24	62.1
25	63.0
26	63.9
27	64.9
28	65.8
29	66.8
30	67.7
31	68.7
32	69.7
33	70.7
34	71.7
35	72.8
36	73.9
37	75.0
38	76.4
39	78.2
40	81.3

### 13.1.4 FATIGUE

Fatigue 8a Adult v1.0	
Raw Score	Scale Score
8	33.1
9	38.5
10	41.0
11	42.8
12	44.3
13	45.6
14	46.9
15	48.1
16	49.2
17	50.4
18	51.5
19	52.5
20	53.6
21	54.6
22	55.6
23	56.6
24	57.5
25	58.5
26	59.4
27	60.4
28	61.3
29	62.3
30	63.3
31	64.3
32	65.3
33	66.4
34	67.5
35	68.6
36	69.8
37	71.0
38	72.4
39	74.2
40	77.8

### 13.1.5 PAIN INTERFERENCE

Pain Interference 8a Adult v1.1	
Raw Score	Scale Score
8	40.7
9	47.9
10	49.9
11	51.2
12	52.3
13	53.2
14	54.1
15	55.0
16	55.8
17	56.6
18	58.1
19	58.1
20	58.8
21	59.5
22	60.2
23	60.8
24	61.5
25	62.1
26	62.8
27	63.5
28	64.1
29	64.8
30	65.5
31	66.2
32	66.9
33	67.7
34	68.4
35	69.2
36	70.1
37	71.0
38	72.1
39	73.5
40	77.0

### 13.1.6 PHYSICAL FUNCTION

Physical Function 10a Adult v2.0	
Raw Score	Scale Score
10	13.5
11	16.6
12	18.3
13	19.7
14	20.9
15	22.1
16	23.1
17	24.1
18	25.0
19	26.0
20	26.9
21	27.7
22	28.6
23	29.4
24	30.2
25	31.0
26	31.8
27	32.5
28	33.3
29	34.0
30	34.8
31	35.5
32	36.3
33	37.0
34	37.8
35	38.5
36	36.3
37	40.1
38	40.9
39	41.7
40	42.6
41	43.5
42	44.4
43	45.5
44	46.6
45	47.9
46	49.4
47	51.2
48	53.4
49	55.8
50	61.9

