#### 3.3 Exploratory Endpoints

- Difference in mean change from baseline for clinical assessments in various affected clinical domains (respiratory, muscle strength and function, dysphagia) using the Pharmacokinetic Set by dose (cohort), for single or multiple administration, and by mutated gene (subcohort) at each post-baseline visit. The parameters to be analyzed for respiratory function are FVC (L), %FVC Predicted, FEV1 (L), %FEV1 Predicted, FEV1/FVC, MEP (cm H2O), %MEP Predicted, MIP (cm H2O), %MIP Predicted, Oxygen Saturation (%). The MyoGrip Test score will be used for analyzing muscle strength. The following parameters will be analyzed for muscle function; D1 Standing and transfers (%), D2 Axial and proximal motor function (%), D3 Distal motor function (%), Total MFM32 Score (%). Dysphagia will be assessed using the EAT-10 total score.
- Difference in mean change from baseline for PROMIS Questionnaire T-scores for the following domains (Anxiety, Depression, Fatigue, Pain Interference, Ability to Participate and Physical Function) using the Pharmacokinetic Set by dose (cohort), for single and multiple administration, and by mutated gene (subcohort) at each post-baseline visit.
- Comparison of proportion of CGI-I responders (responders defined as responding 1 or 2) using the Pharmacokinetic Set by dose (cohort), for single and multiple administration, and by mutated gene (subcohort) at each post-baseline visit.
- Comparison of proportion of PGI-C responders (responders defined as responding 1 or 2) using the Pharmacokinetic Set by dose (cohort), for single and multiple administration, and by mutated gene (subcohort) at each post-baseline visit.
- Comparison of proportion of Goal Attainment Scaling (GAS) Questionnaire responders (responders defined as responding ‘YES – MUCH BETTER’, ‘YES – A LITTLE BETTER’) using the Pharmacokinetic Set by dose (cohort), for single and multiple administration, and by mutated gene (subcohort) at each post-baseline visit.
- Comparison of means of ADA against DYN101 using the Pharmacokinetic Set by dose (cohort), for single and multiple administration, and by mutated gene (subcohort) at each post-baseline visit.
- Comparisons of the metabolic profile of DYN101 in blood and urine using the Pharmacokinetic Set by dose (cohort), for single and multiple administration, and by mutated gene (subcohort) at each post-baseline visit.

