#### 4 SAMPLE SIZE

Sufficient subjects will be screened to ascertain approximately 18 subjects who will be dosed and finish the trial. The target is approximately 6 subjects per dose level. In each dose level, the target will be up to 6 subjects with a DNM2 mutation and up to 3 subjects with an MTM1 mutation. This sample size is deemed to be appropriate for safety and tolerability purposes and are not based on any power analysis.

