### 6.2.13 Pharmacodynamic data

#### Patient-Reported Outcomes Measurement Information System (PROMIS) Questionnaire

Summary T-score for each domain (Anxiety, Depression, Fatigue, Pain Interference, Ability to Participate and Physical Function) will be calculated. Scoring is done by calculating total raw scores for each domain by summing subject's answers. Missing values are not allowed and if any data missing for a domain then total raw score will not be calculated. After raw scores are calculated a scoring table will be used to translate the total raw score into a T-score for each subject. Scoring tables are shown in the [Appendix](#) of this document.

For Physical Function, NHS part of the study utilized different PROMIS scale. First question was ‘Can you walk 25 feet on a level surface (with or without support)?’. If subject answered ‘Yes’ then he/she filled all the following 12 questions. If subject answered ‘No’ then only 6 further questions were filled.

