## **6.13 Pharmacodynamic and Exploratory Efficacy Analyses**

### **6.13.1 PROMIS Questionnaire**

Patient-Reported Outcomes Measurement Information System (PROMIS®) is a National Institutes of Health Initiative, created to assess patient-reported health status for physical, mental, and social well-being to reliably and validly measure patient-reported outcomes in chronic diseases for clinical research and practice. The PROMIS domains tested in this trial are Anxiety (8 items), Depression (8 items), Fatigue (8 items), Pain Interference (8 items), Ability to Participate (8 items) and Physical Function (10 items).

Descriptive statistics (n, mean, SD, median, min, max) for observed values and changes from baseline in T-scores will be presented by treatment group (cohort, subcohort) at each visit for each domain score.

All data, including responses to questionnaire items and T-scores, will be listed.

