## **10 CHANGES TO PLANNED PROTOCOL ANALYSIS**

Additional exploratory Bayesian analyses for MFM 32, continuous respiratory measures and continuous strength measures were added in section [6.13.10](#).

The study was stopped and the final reporting will be including only the IDMC outputs and selected efficacy parameters (FVC, MIP, Total MFM32 Score and PGI-C).

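### The SAP's Physical Function 10a conversion table is out of order at raw score 36, so a raw rise from 33, 34 or 35 to 36 lowers the T-score; Pain Interference 8a has a lesser irregularity at raw 18

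*SAP*

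**What the plan says.** SAP 6.2.13 sums a subject's item answers within each PROMIS domain, after which "a scoring table will be used to translate the total raw score into a T-score for each subject". The tables are in SAP 13.1. Those at issue are "Physical Function 10a Adult v2.0" in 13.1.6 and "Pain Interference 8a Adult v1.1" in 13.1.5.

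The T-scores feed a planned exploratory endpoint. SAP 3.3 lists "Difference in mean change from baseline for PROMIS Questionnaire T-scores for the following domains", and the domains named there include Physical Function and Pain Interference. SAP 6.13.1 summarises the T-scores descriptively and adds that "changes from baseline in T-scores will be presented by treatment group (cohort, subcohort) at each visit for each domain score".

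The trial was terminated early. SAP Section 1 says that the document still contains all planned analyses, but that only an abbreviated CSR will be written and not every analysis will be run. SAP Section 10 limits the final reporting to the IDMC outputs and "selected efficacy parameters (FVC, MIP, Total MFM32 Score and PGI-C". PROMIS is not in that list, and its listing (16.2.6.1) is struck through in Section 12.

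**The concern.** A table that converts a sum score to a T-score should keep the order of the raw scores. As printed, Physical Function 10a does not. A subject whose raw sum rises to 36 from 33, 34 or 35 receives a lower T-score, and a subject who falls from 36 to one of those values receives a higher one. The SAP does not state which direction on this scale is better, but the order is inverted either way. Change from baseline would then carry the wrong sign for those subjects.

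Routine validation may not catch this. Section 12 names independent programming for the PROMIS table, but two programmers who both take the look-up from this appendix will agree on the same value.

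Pain Interference 8a is a weaker case. Two adjacent raw scores share one T-score, so a real one-point change between them is scored as none.

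**Working it through.** **Inputs.** All nine conversion tables in SAP 13.1, as printed; group sizes from SAP Section 4 ("The target is approximately 6 subjects per dose level", with up to 3 *MTM1* subjects in each).

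**Step 1: test every table for strict increase.** Seven of the nine tables increase strictly throughout. Physical Function 10a and Pain Interference 8a each fail at one place.

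**Step 2: Physical Function 10a around raw 36.**

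| Raw | Printed T-score | Step from previous raw score |
|---|---|---|
| 32 | 36.3 | +0.8 |
| 33 | 37.0 | +0.7 |
| 34 | 37.8 | +0.8 |
| 35 | 38.5 | +0.7 |
| 36 | 36.3 | -2.2 |
| 37 | 40.1 | +3.8 |
| 38 | 40.9 | +0.8 |

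Scored change when the raw sum rises to 36:

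- from 32: 36.3 - 36.3 = 0.0
- from 33: 36.3 - 37.0 = -0.7
- from 34: 36.3 - 37.8 = -1.5
- from 35: 36.3 - 38.5 = -2.2

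**Step 3: size of the departure.** Order is restored by any value strictly between 38.5 and 40.1. The midpoint is (38.5 + 40.1)/2 = 39.3, and 36.3 - 39.3 = -3.0. With 39.3 in place, the step from 35 to 36 is 39.3 - 38.5 = +0.8 and the step from 36 to 37 is 40.1 - 39.3 = +0.8, in line with the rows around them.

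**Step 4: Pain Interference 8a around raw 18.**

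| Raw | Printed T-score | Step from previous raw score |
|---|---|---|
| 16 | 55.8 | +0.8 |
| 17 | 56.6 | +0.8 |
| 18 | 58.1 | +1.5 |
| 19 | 58.1 | 0.0 |
| 20 | 58.8 | +0.7 |

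The midpoint of raw 17 and raw 19 is (56.6 + 58.1)/2 = 57.35, and 58.1 - 57.35 = +0.75. No pair of raw scores is reversed.

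**Step 5: are these gaps unusual?** Each entry was compared with the midpoint of its two neighbours, leaving out the two entries at each end of every table. Raw 36 in Physical Function 10a departs by 3.0 and raw 18 in Pain Interference 8a by 0.75. Setting aside the rows next to those two cells, which are distorted by them, the largest departure anywhere else is 0.45 (Depression 8a, raw 10).

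**Step 6: effect on a group mean.** Suppose that one subject is at raw 36 at a visit and the right value is 39.3. The group mean is then too low by 3.0/6 = 0.5 T-score points with 6 subjects, and by 3.0/3 = 1.0 with 3. If that subject is at raw 36 at baseline instead, the mean change is too high by the same amount.

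**The case against.** The strongest reply is that no output kept in the reporting is shown to use these tables. SAP Section 8 drops the planned primary and final analyses, Section 10 leaves PROMIS out, and the PROMIS table (14.2.1.1) has no IDMC meeting marked against it. In the text as read, that table carries no strikethrough although its listing does. The same is true of CGI-I and GAS, so this looks like lost formatting, and Section 10 settles the matter. Section 1's statement that all planned analyses remain in the document has to be read with its next sentence, which says that not all will be performed. A reader might infer that reported trial results are wrong; the documents do not support that. What remains is that 6.2.13, 6.13.1 and the appendix still stand as the scoring rule, and Section 6 allows further tables in the CSR if the data warrant them.

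A second reply is that one digit may have been misread from the PDF: 39.3 and 36.3 differ by a single character. This cannot be excluded, and it is why the SAP source file should be checked first. It explains the Pain Interference cell less well, since 57.3 or 57.4 does not become 58.1 by one digit.

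Third, the PROMIS scoring manual is not among the documents. A reader might take 39.3 and 57.35 as the true values, but they are interpolations. A reader might also infer that both tables can reverse the sign of a change. Only Physical Function does. The Pain Interference error is inferred from an uneven step, and nothing in the SAP says that the tables must increase strictly.

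**Conclusion.** The point holds, at low severity. As printed, the Physical Function 10a table is out of order at one of its 41 raw scores, and it gives the wrong sign to a raw change between 36 and 33, 34 or 35. This follows from the printed entries alone. The size of the error, about 3.0 T-score points, assumes that the true entry is near the midpoint of its neighbours; strict order requires only that it lie between 38.5 and 40.1. The Pain Interference 8a entry at raw 18 is probably about 0.75 too high on the same assumption, with a tie and no reversal.

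The reach is narrow. The endpoint is exploratory and descriptive, only subjects at these raw scores are touched, and safety, PK and the retained efficacy parameters do not depend on the tables. The point matters for any PROMIS T-score derived under SAP 6.2.13, or in a later analysis that reuses the appendix.

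**What to change.** Check Physical Function 10a raw 36 and Pain Interference 8a raw 18 against the SAP source file, the PROMIS scoring manual and any look-up already programmed. Replace the cells with the manual's values, not with the interpolations given here. Then run a strict-increase check on all nine appendix tables before any T-score is derived or listed. If a look-up has already been built from the appendix, re-derive the T-scores for subjects at these raw scores.

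The cost is two table cells and a short programmed check. If no PROMIS T-score is ever derived, a note of correction to the appendix is enough.
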